Statistical Analysis Plan

Effects of a Modified Hospital Elder Life Program in Abdominal

Surgery Patients

Study Hospital: National Taiwan University Hospital, Taiwan, Taiwan

Principal Investigator: [name] [name], DNSc

Co-Investigator & Collaborator:

[name] [name], PhD [name], PhD [name], PhD [name] [name], PhD [name], PhD, [name], PhD [name], PhD [name], MSN, graduate student [name], MSN, PhD student [name] [name] student [name], MPH

NCT number: NCT 01045330

September 27, 2017

Sample Size and Power Calculation

The effect of NTU-HELP in preventing functional decline will be evaluated by the following mixed effects models:

 $g(y_{it}) = [] + a_i + []_1 * (studied-ward indicators)_i + b_i * (studied-ward indicators)_i + b_i$

$$\boxed{}_{2}^{*} \operatorname{time}_{t} + \boxed{}_{3}^{*} \operatorname{time}_{t}^{2} + c_{i}^{*} \operatorname{time}_{t} + \boxed{}_{4}^{*} (\operatorname{confounders})_{it} + \boxed{}_{5}^{*} (\operatorname{treatment group})_{i} + \boxed{}_{t}$$

i=1,...,n (# of patients); t=1,...,5 (time points),

where y_{it} is the "continuous" outcome measurement (with transformation g(.) whenever is needed), a_i is a random intercept (with mean 0) designating a different baseline outcome value for a patient, b_i is a random slope (with mean 0) indicating different studied-ward effects for different patients, c_i is another random slope indicating different tendencies to decline (or recover) over time for different patients, and \Box_t is the random error. The fixed regression coefficient \Box_1 is the overall studiedward effect. The fixed regression coefficients \Box_2 and \Box_3 describe the overall pattern of the outcome measures across time. The fixed regression coefficient \Box_4 describes the effects of confounding variables. *The fixed regression coefficient* β_5 *is our major interest and indicates the effect of the HELP intervention.*

The sample size projections are constructed for testing the significance of the treatment effect \Box_5 in the proposed mixed effects model (i.e., H₀: $\Box_5=0$ versus H₁: $\Box_5\neq 0$). For simplicity, we assume there is no studied-ward multi-level effect for the sample size calculation (i.e., b_i=0). We use the "Optimal Design" Software Version 1.77 for the calculation (https://sites.google.com/site/optimaldesignsoftware/home). This software provides sample size and power estimation for developing an optimal

design for multi-level and longitudinal research. When implementing the OD software, we need to set up (1) the standardized effect size δ (the estimated treatment effect divided by the standard error of the outcome), (2) the within-patient variance σ^2 , (3) the between-patient variance τ , (4) the number of repeated measurements per patient M, and (5) the significance level []. We use the standardized effect size δ =0.35, which is considered "worth detecting" according to Cohen's rules,⁶⁵ σ^2 =1, τ =1, M=5 and []=0.05. The plot of power versus the estimated patient numbers is shown in the following. From the plot, it will require 170 patients if for 60% power, 215 patients if for 70% power, 270 patients if for 80% power, and 360 patients if for 90% power. Considering the attrition and the future need for more complicated model building (i.e., more covariates into the mixed effects model, more complicated mixed effects model, approaches for categorical outcome measurements), we propose to recruit **350** patients to achieve above 80% power.

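### The model leaves the baseline outcome to a mean-zero random intercept, which does not adjust β5 for it; a fixed baseline covariate would recover precision at almost no cost

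*SAP*

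**What the plan says.** The section Sample Size and Power Calculation writes the model out and explains each term. The starting level of the outcome appears once, in the explanation of the intercept: "a_i is a random intercept (with mean 0) designating a different baseline outcome value for a patient". A second random term covers time trends: "c_i is another random slope indicating different tendencies to decline (or recover) over time for different patients". Of the coefficient β4 the SAP says that it "describes the effects of confounding variables", without listing those variables. The treatment coefficient β5 multiplies a patient-level group indicator, does not vary with time, and "is our major interest and indicates the effect of the HELP intervention".

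The indices are "i=1,...,n (# of patients); t=1,...,5 (time points"; whether occasion 1 precedes the intervention is not stated. The model has no fixed term for the baseline value, no treatment-by-time term, and no constraint that the arms share a baseline mean. The sample size paragraph sets σ² = 1, τ = 1, M = 5 and δ = 0.35, and proposes 350 patients.

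**The concern.** A mean-zero random intercept that is independent of arm describes how a patient's measurements hang together. It does not condition the arm comparison on where patients started. β5 is a between-patient contrast and so carries the full between-patient variance τ.

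The consequence depends on what occasion 1 is, but neither reading removes it:

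- **Occasion 1 is baseline.** It sits among the outcomes, and any baseline difference between arms is averaged into β5.
- **All five occasions are later.** The baseline value, usually a strong predictor of later function, does not enter the analysis.

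At stake are precision that the trial's own data may supply and the stability of β5 when the arms start unequal.

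**Working it through.** **Inputs from the SAP:** τ = 1, σ² = 1, M = 5, δ = 0.35, α = 0.05 with a two-sided alternative, N = 350.

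**Assumed, because the SAP does not say:** randomisation; 1:1 allocation; τ is the random-intercept variance; 0.35 is in units where τ = 1; slope variance s of c_i is 0 at first, then varied, with slope independent of intercept. The ward slope b_i is 0, as in the SAP's own calculation.

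**1. The plan's own figure.** N = 4V(z₀.₉₇₅ + z_power)²/δ². For a constant β5 over five occasions, V = τ + σ²/5 = 1.2, so 80% power needs 4 × 1.2 × 7.849/0.1225 = 308, not the stated 270. The stated 170/215/270/360 match a linear-change formula, V = τ + 12σ²/[(M−1)M(M+1)], evaluated at six occasions: V = 1.057 and N = 169/213/271/363. At five occasions V = 1.10 and N = 282. That mismatch is a separate matter. Here it shows only that reading τ = 1 as an intercept variance is an assumption.

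**2. Same contrast, with and without baseline (s = 0).** The variance of an arm difference is 4V/N. For m post-intervention occasions, V = τ + σ²/m unadjusted and V = τ + σ²/m − τ²/(τ + σ²) adjusted.

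- Four later occasions: 1 + 0.25 = 1.25, falling to 1.25 − 0.5 = 0.75 (−40%).
- Five later occasions plus a separate baseline: 1.20 to 0.70 (−42%).
- SE for four occasions at N = 350: 2√(1.25/350) = 0.120, falling to 2√(0.75/350) = 0.093.
- Power for 0.35: 83%, rising to 97%.

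**3. Dependence on the assumptions, same contrast.** The variance is multiplied by 1 − ρ², where ρ is the correlation of baseline with the later mean. The cut is 4% at ρ = 0.2, 9% at 0.3 and 25% at 0.5. With a random slope and time coded 0–4, the mean of occasions 2–5 has V = 1.25 + 6.25s, and adjustment still removes 0.5:

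- s = 0.05: 1.5625 to 1.0625 (−32%).
- s = 0.10: 1.875 to 1.375 (−27%).

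**4. Against β5 as written, if occasion 1 is baseline.** Generalised least squares on the written model (time 0–4), compared with the best baseline-adjusted estimate from occasions 2–5:

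| Slope variance | Weight of occasion 1 in β5 | V, written | V, adjusted | Change |
|---|---|---|---|---|
| 0 | 0.20 | 1.200 | 0.750 | −37.5% |
| 0.05 | 0.33 | 1.333 | 1.000 | −25% |
| 0.10 | 0.40 | 1.400 | 1.167 | −17% |
| 0.25 | 0.49 | 1.486 | 1.444 | −3% |
| 1 | 0.56 | 1.564 | 1.792 | +15% |

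The written β5 gains its low variance at large s by leaning on a pre-intervention value. A constant post-intervention effect Δ then appears in it only as (1 − weight) × Δ: 0.80Δ at s = 0 and 0.44Δ at s = 1. Per unit of Δ, the root of V at s = 1 is √1.564/0.436 = 2.87 for the written β5 and √1.792 = 1.34 for the adjusted estimate.

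**5. Sensitivity to imbalance (s = 0).** One unit of baseline difference moves β5 by τ/(τ + σ²) = 0.5 if all five occasions are later, and by 0.2 × 1 + 0.8 × 0.5 = 0.6 if occasion 1 is baseline. Simulation gave 0.50 and 0.61.

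**The case against.** **The size depends on switching off a planned term.** The 40% needs the variance of c_i to be zero, and it compares two versions of a post-intervention mean, neither of which is the five-occasion β5 if occasion 1 is baseline. This stands. A reader might infer that the planned β5 itself wastes 40% of its variance; step 4 shows that this fails once slopes vary. The documents give no slope variance, and the stated sample sizes fit a slope calculation better than a level one, so τ = 1 may not be an intercept variance at all.

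**Randomisation is not stated.** This also stands. A reader might infer an inflated false-positive rate. Under randomisation the overall rate is 5%. Higher rates arise only among trials selected for a large imbalance, and the SAP does not state the design on which such figures rest. Without randomisation the 5% has no stated basis either, and baseline adjustment matters more.

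**The covariate may be among the confounders.** They are unlisted, and the SAP foresees "more covariates into the mixed effects model, more complicated mixed effects model". So the baseline value is not excluded. But the only place the SAP gives it is a_i, and listing it as a confounder while occasion 1 remains an outcome would put it on both sides of the equation. The open list does not settle the matter.

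**It overlaps with the choice of contrast.** If occasion 1 is baseline, dropping it from the outcomes does change what β5 measures. Steps 2 and 3 hold the contrast fixed, and the gain remains. Nor does the SAP say outright that a baseline measurement is taken; the fix presumes one.

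**Conclusion.** The point holds as one of precision and robustness, not validity. As written, the model does not adjust β5 for baseline. On the same post-intervention mean, adjustment would cut the variance by about 40% with τ = σ² = 1 and no slope variance, by 32% or 27% at slope variance 0.05 or 0.10, and by ρ² in general. Measured against the written five-occasion β5, the cut is 37.5% at zero slope variance, about 3% at 0.25, and reverses at 1. That reversal reflects a pre-intervention value counted as outcome, not better information on the effect. All figures assume randomisation, 1:1 allocation and the reading of τ given above. If baseline predicts later values poorly, for instance because the scale is near its ceiling before surgery, the gain is small.

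**What to change.** In the model for β5:

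- Add the patient's pre-intervention value of the same outcome, on the g scale, as a fixed covariate.
- Keep only post-intervention occasions on the left-hand side, and say which these are (t = 2–5 if occasion 1 is baseline).
- Redefine a_i as the between-patient difference that remains after baseline.
- State a rule for missing baseline values, such as mean imputation of the covariate.

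The cost is one model term and some wording. No extra patients are needed and, provided the pre-intervention value is collected, no new data. β5 will then rest on post-intervention occasions only. For this point, the 350 patients and the text that justifies them can stay.

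### Minor, free improvement: entering the five occasions as a factor keeps misfit of the quadratic time course out of β5 should attrition differ between arms

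*SAP*

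**What the plan says.** The section Sample Size and Power Calculation of the SAP sets out one mixed effects model for continuous outcomes, indexed by "i=1,...,n (# of patients); t=1,...,5 (time points").

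- **Mean course.** It has a linear and a squared term in time, shared by all patients. Their coefficients "describe the overall pattern of the outcome measures across time".
- **Patient-specific part.** There is a random intercept a_i, a random studied-ward effect b_i, and c_i, which "is another random slope indicating different tendencies to decline (or recover) over time for different patients".
- **Treatment.** The group enters once, as a main effect. Its coefficient β5 "is our major interest and indicates the effect of the HELP intervention".
- **Attrition.** It appears once, as one of two reasons for recruiting 350: "Considering the attrition and the future need for more complicated model building". No rate, timing, mechanism or difference between arms is given.

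The SAP does not give the timing of the five occasions, how time is coded, or the expected shape of the mean course.

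**The concern.** Two coefficients cannot follow every pattern over five occasions. A quadratic can fall and then rise, but it bends smoothly. A one-step drop followed by a recovery that levels off leaves it too high at some occasions and too low at others. That course is plausible for abdominal surgery patients if the first occasion precedes the operation.

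When both arms contribute the same mix of occasions, these errors are the same in each arm and cancel in the comparison. When one arm loses more patients, its data lean more towards the early occasions. Because β5 is the only arm-specific term, it takes up the difference in average misfit. What is at stake is whether the coefficient of main interest could partly reflect which arm kept more patients. Whether treatment should interact with time is a separate question.

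**Working it through.** **Inputs from the SAP:** five occasions, σ²=1, τ=1, two-sided test at 0.05, N=350, δ=0.35.

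**Assumptions, none stated in the SAP:** true effect zero; 1:1 allocation; equally spaced occasions unless noted; mean course (0, −1, −0.5, −0.2, −0.1) times a drop of 1 or 2 total SDs, the total SD being √(1+1)=1.414; retention 70%/84% or 60%/85%; δ read in units of σ=1.

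**1. Benchmark.** The SAP gives no figure for bias. The SE of β5 with complete data is √[4(τ+σ²/5)/N] = √(4×1.2/350) = 0.117. (With the same variance, 80% power needs 4×1.2×(1.960+0.842)²/0.35² = 308 patients, against 270 in the SAP. That is a separate matter and nothing below uses the 270.)

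**2. Misfit of the quadratic.** Least squares on the unit course, with times −2 to 2: mean −1.8/5 = −0.36; linear coefficient 0.6/10 = 0.06; quadratic coefficient 2.0/14 = 0.143 on the contrast (2, −1, −2, −1, 2).

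| Occasion | 1 | 2 | 3 | 4 | 5 |
|---|---|---|---|---|---|
| Course | 0 | −1 | −0.5 | −0.2 | −0.1 |
| Fitted | −0.194 | −0.563 | −0.646 | −0.443 | 0.046 |
| Misfit | 0.194 | −0.437 | 0.146 | 0.243 | −0.146 |

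The misfit averages zero over all five occasions, but (0.1943−0.4371)/2 = −0.1214 over the first two.

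**3. Transfer to β5, by hand.** Suppose all dropout follows occasion 2. With random intercepts only, a patient with m occasions has weight m/(σ²+mτ): 2/3 for m=2 and 5/6 for m=5. Holding the curve of step 2 fixed, an arm with retention p carries an average misfit of

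−0.1214 × (1−p)(2/3) / [(1−p)(2/3) + p(5/6)].

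- 70%: −0.1214×0.200/0.783 = −0.0310. 84%: −0.1214×0.107/0.807 = −0.0161. Difference 0.0149, or 0.021 for a 1-SD drop (×1.414) and 0.042 for 2 SD.
- 60%: −0.1214×0.267/0.767 = −0.0422. 85%: −0.1214×0.100/0.808 = −0.0150. Difference 0.0272, or 0.038 for 1 SD and 0.077 for 2 SD.
- Equal retention: the two terms are identical and the difference is zero.

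**4. Full model fits.**

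- *All dropout after occasion 2, random intercept and slope fitted, large simulated samples scaled to N=350.* For 70%/84%: 0.017 to 0.024 (1 SD) and 0.032 to 0.044 (2 SD). For 60%/85%: 0.044 to 0.046 and 0.066 to 0.080.
- *Same dropout, exact generalised least squares.* 0.02 to 0.09 across these cases without a random slope, and up to about 0.12 with one.
- *Dropout spread over the occasions.* About 0.
- *Other curves and timings, 10% v 30% loss, 1.5-SD drop.* 0.010 to 0.015 with equal spacing; 0.052 to 0.056 with times 0, 1, 2, 6, 26 entered as calendar time.
- *Uneven times, other dropout patterns.* 0.00 to 0.03 in one set of runs, and the sign can reverse.
- *Equal attrition of 20% or 40%.* Bias 0.000 and error 5.0%, however poor the fit.

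**5. Effect on the test.** The two-sided error is Φ(−1.96+b/SE)+Φ(−1.96−b/SE). With SE near 0.12:

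- b=0.02: ratio 0.17, error about 5.3%.
- b=0.06: ratio 0.50, 0.072+0.007, about 8%.
- b=0.12: ratio 1.0, 0.169+0.002, about 17%.

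**6. Precision.** At equal 77% retention, with dropout depending on the observed score, the SE is 0.1222 (quadratic) v 0.1200 (factor) for a 1-SD drop, and 0.1237 v 0.1198 for 2 SD. The ratios are 1.02 and 1.03. Under completely random dropout the difference is below 1%.

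**7. Visit indicators.** In the exact calculations, bias is 0.000 and error 5.0% in every scenario, with an SE practically equal to the quadratic model's. In the simulations, β5 stayed at or below 0.009.

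**The case against.** A quadratic mean with a random slope is a standard specification, and nothing the SAP says about it is false or contradictory. A parabola can itself show decline and then recovery. Level and linear trend vary by patient through a_i and c_i, so only the mean curvature is shared. The SAP also foresees more complex models. All of this stands, and it is why the point is a suggestion. The random terms do not remove the effect, however: the fits above included them and the bias remained.

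A reader might infer three stronger things, which the SAP does not support.

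- *That the attrition the plan anticipates will bias β5.* The plan mentions attrition without a rate or a difference by arm, and equal attrition gives no bias.
- *That the SAP itself describes a mean decline followed by recovery.* The words "indicating different tendencies to decline (or recover) over time for different patients" define c_i and concern variation between patients. The baseline value in the text defines the random intercept and does not place occasion 1 before surgery.
- *That 270/350 = 77% is the planned retention.* The margin also covers more complicated model building, so 77% is only an illustrative value here.

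**Conclusion.** The point holds conditionally and is minor. Misfit of the quadratic can enter β5 only if the true course is not quadratic and the arms also contribute different mixes of occasions. The SAP establishes neither condition and excludes neither.

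Under the assumptions above, the spurious β5 is about 0 to 0.06 for 70%/84% retention, at most 0.06/0.35 = 17% of the planned effect. It reaches about 0.12, or 34%, for 60%/85% with a 2-SD drop. These values illustrate and do not bound: they depend on when patients leave, on visit spacing and on a random-slope variance that the SAP does not give, and the sign can vary. In the moderate equally spaced cases the error rate stays between 5% and 7%.

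A general loss of precision should not be inferred either. The 2–3% SE penalty appeared only under outcome-dependent dropout. The case for changing the model is that the shape assumption is unnecessary with five fixed occasions and costs almost nothing to remove from the main test.

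**What to change.** In the fixed part of the model, replace β2·time + β3·time² with four visit indicators (occasions 2 to 5 against occasion 1). Keep treatment group, studied-ward, confounder and random terms as they are. Use this as the main model for every continuous outcome, and keep the quadratic curve as a descriptive summary if wanted.

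The cost is one line of SAP wording and two more fixed parameters (four instead of two) with 350 patients. No new data and no change in trial conduct are needed.

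### The effect size δ=0.35 is scaled by a standard error, and the stated 270 patients for 80% power on β5 does not follow from the stated inputs (156 or 310 on the two usual SD readings)

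*SAP*

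**What the plan says.** Everything is in the SAP section Sample Size and Power Calculation.

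- **Target.** "The sample size projections are constructed for testing the significance of the treatment effect" β5, two-sided. β5 is the coefficient of treatment group in a mixed model with five time points. The model has no treatment-by-time term, so β5 is a constant group difference.
- **Scale of the effect.** δ is defined as "the estimated treatment effect divided by the standard error of the outcome".
- **Inputs.** "We use the standardized effect size δ =0.35", with "σ^2 =1, τ =1, M=5 and []=0.05". For the calculation, "we assume there is no studied-ward multi-level effect for the sample size calculation".
- **Result, read from a plot.** "it will require 170 patients if for 60% power, 215 patients if for 70% power, 270 patients if for 80% power", and 360 for 90%.
- **Decision.** Recruit 350 "patients to achieve above 80% power", the excess being for attrition and for more complex models later.

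**The concern.** There are two problems.

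First, the definition cannot work as written. A standard error shrinks as the sample grows, so an effect expressed in standard errors does not determine a sample size. If the term is loose wording for a standard deviation, the SAP still does not say which one. With σ²=1 and τ=1 the choice matters: the within-patient and between-patient SDs are both 1, while the SD of a single outcome is √2=1.41.

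Second, the four stated sample sizes should follow from the stated inputs and the stated parameter, and on the usual readings they do not. A reader therefore cannot tell what size of effect 270 patients would detect, whether the calculation concerned β5 at all, or how much of the step from 270 to 350 is really available for attrition.

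**Working it through.** **Inputs from the SAP.** δ=0.35, σ²=1, τ=1, M=5, α=0.05 two-sided, no ward effect, β5 as target.

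**Assumptions, because the SAP does not state them.** 1:1 allocation, and τ as the variance of a random intercept.

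**Formula.** For a constant group difference Δ, each patient contributes the mean of five measurements, with variance v = τ + σ²/M = 1 + 1/5 = 1.2. Power comes from a noncentral F with 1 and n−2 degrees of freedom and noncentrality nΔ²/(4v).

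**Trying to reproduce the SAP's figures for β5**

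| Reading of δ | Δ | n for 60 / 70 / 80 / 90% power | Power at 270 |
|---|---|---|---|
| SAP as stated | – | 170 / 215 / 270 / 360 | 80% |
| Units of √τ (or √σ²), SD = 1 | 0.35 | 193.9 / 243.8 / 309.5 / 413.6 | 74.4% |
| Outcome SDs, √(τ+σ²) = √2 | 0.35×√2 = 0.495 | 97.9 / 122.9 / 155.7 / 207.8 | 95.9% |
| SD of the five-visit mean, √1.2 | 0.35×√1.2 = 0.383 | 161.9 / 203.5 / 258.2 / 345.0 | 81.7% |

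Hand check of the second row at 80%, normal approximation: 4×1.2×(1.960+0.842)²/0.35² ≈ 308, against 310 from the F distribution. A simulation of 40,000 trials on patient means gave 74.4% power at 270 and 80.3% at 310 for Δ=0.35, and 80.1% at 156 for Δ=0.495.

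**What variance do the stated figures imply?** Solving for v with Δ=0.35 gives 1.051, 1.057, 1.046 and 1.044 at the four powers. The values agree closely with one another and are not 1.2. The other two readings, expressed on the same scale, correspond to v = 1.2/2 = 0.6 and 1.2/1.2 = 1.

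**Could plot-reading error explain it?** Allowing ±5 patients on each figure, the implied v ranges over 1.019–1.082, 1.032–1.082, 1.026–1.065 and 1.029–1.058. None of these ranges includes 0.6, 1 or 1.2, although the first comes close to 1.

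**What would give figures like these?** Contrasts describing change over time, with τ as the variance of that change:

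- Linear slope, five occasions: v = 1 + 1/10 = 1.1; n ≈ 178 / 224 / 284 / 380.
- Linear slope, six occasions: v = 1 + 1/17.5 = 1.057; n ≈ 171 / 215 / 273 / 365.
- Quadratic contrast (unscaled coefficients 2, −1, −2, −1, 2), five occasions: v = 1 + 1/14 = 1.071; n ≈ 173 / 218 / 276 / 369.

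The last two lie within about 3% of all four stated figures. Neither is β5.

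**Consequence for 350**

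| Reading | Power at 350 | At 315 (10% lost) | At 280 (20% lost) |
|---|---|---|---|
| √τ units | 84.6% | 80.7% | 75.9% |
| Outcome SDs | 98.8% | 97.9% | 96.5% |

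The attrition rates are illustrative, since this section gives none. The margin above the 80% requirement is (350−270)/350 = 22.9% on the SAP's figure and (350−310)/350 = 11.4% on the √τ reading.

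**The case against.** The strongest reply is that δ may be scaled by the SD of a patient's five-visit mean, which is arguably the nearest thing to a standard error of the outcome. On that reading 270 patients give 81.7% power for β5, so the SAP's claim would be met and the gaps of 4–6% could be put down to reading a plot. This does not fully stand. All four gaps are in the same direction, and an error of ±5 patients does not close any of them, though it nearly does at 60% power. Under this reading σ², τ and M also drop out of the calculation, whereas the SAP says they had to be set.

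A second reply is that the software's own definitions of δ and τ are not visible in the SAP text, and that the plot, which may show its settings, is missing from the text reviewed. That stands. The check shows that the stated figures do not follow from the SAP as worded; it does not show that the software run was faulty. For the same reason the change-over-time fits are only suggestive: two different contrasts fit four rounded numbers about equally well, and one of them keeps five occasions. It cannot be concluded that M differed from 5.

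A third reply is that little depends on it. That stands in part. Before attrition, 350 exceeds 80% on every reading above. Power falls below 80% only on the √τ reading, and only once losses pass about 11%. The 80 extra patients were also meant to cover model complexity, not attrition alone.

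**Conclusion.** The point holds. The scale of δ is wrongly defined, and the stated series of sample sizes does not follow from the stated inputs for β5: 80% power needs 310 patients in √τ units or 156 in outcome SDs, against the stated 270. This rests on 1:1 allocation, a random-intercept τ and no separate variance for the patient-specific time slope. Which setting produced 270 cannot be determined from the text. The target of 350 is not undermined before attrition, so this is a correction that should be made rather than a threat to the trial. Confidence is medium because the software's definitions are not in the document.

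**What to change.** In Sample Size and Power Calculation:

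1. Replace the standard error in the definition of δ with the named SD that scales it.
2. State whether τ is the variance of a random intercept or of a slope.
3. State which effect was tested in the software, and confirm that it is β5 with M=5. If it was a change over time, rerun the calculation for β5.
4. Give the allocation ratio used, then restate the sample sizes and the power at 350, before and after the assumed attrition. If √τ units and a random intercept apply, for instance, the entries would be 310 for 80% power and about 85% at 350. This is an example, not a presumed correction.
5. Translate the detectable effect into outcome SDs only if τ is a random-intercept variance.

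The cost is a wording change and one rerun of the power calculation. Recruitment of 350 need not change.
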